5.1.1 Management (dose Modifications and dose delays) for Treatment-Related Toxicity

All toxicities will be graded according to National Cancer Institute's (NCI's) Common Terminology Criteria for Adverse Events (CTCAE) (NCI CTCAE v 5). The study investigator will determine if either or both medications should be held.

Dose reductions for AEs related to TAS 102 are permitted dose reductions to a minimum dose of 20mg/m² twice a day in 5mg/m² steps. After dose reduction, escalation of dose is not allowed.

Table 1. TAS 102 dose modifications

TAS 102 dose (BID)	BSA (m ²)*	Dosage in mg (BID)	Total daily dose (mg)	Tablets per dose	
				15mg	20mg
Starting dose					
35mg/m ²	<1.07	35	70	1	1
	1.07-1.22	40	80	0	2
	1.23-1.37	45	90	3	0
	1.38-1.52	50	100	2	1
	1.53-1.68	55	110	1	2
	1.69-1.83	60	120	0	3
	1.84-1.98	65	130	3	1
	1.99-2.14	70	140	2	2
	2.15-2.29	75	150	1	3
	≥ 2.30	80	160	0	4
Level 1 dose reduction: from 35mg/m ² to 30mg/m ²					
30mg/m ²	<1.09	30	60	2	0
	1.09-1.24	35	70	1	1
	1.25-1.39	40	80	0	2
	1.4-1.54	45	90	3	0
	1.55-1.69	50	100	2	1

	1.70-1.94	55	110	1	2
	1.95-2.09	60	120	0	3
	2.10-2.28	65	130	3	1
	≥ 2.29	70	140	2	2
Level 2 dose reduction: from 30mg/m ² to 25mg/m ²					
25mg/m ²	<1.10	25	50	2 (PM)¶	1 (AM)¶
	1.10-1.29	30	60	2	0
	1.30-1.49	35	70	1	1
	1.50-1.69	40	80	0	2
	1.70-1.89	45	90	3	0
	1.90-2.09	50	100	2	1
	2.09-2.29	55	110	1	2
	≥ 2.30	60	120	0	3
Level 3 dose reduction: from 25mg/m ² to 20mg/m ²					
20mg/m ²	<1.14	20	40	0	1
	1.14-1.34	25	50	2 (PM)¶	1 (AM)¶
	1.35-1.59	30	60	2	0
	1.60-1.94	35	70	1	1
	1.95-2.09	40	80	0	2
	2.10-2.29	45	90	3	0
	≥ 2.29	50	100	2	1

* Calculate BSA to 2 decimal places.

¶ At a total daily dose of 50mg, patients should take 1 x 20mg tablet in the morning and 2 x 15mg tablets in the evening.

Dose reductions of ramucirumab will be allowed only for proteinuria with 6 mg/kg for first episode of proteinuria (> 2 g/24 hours) and with 5 mg/kg for second episode of proteinuria (> 2 g/24 hours). Only dose delay will be allowed for the other AEs related to ramucirumab.

Table 2. Ramucirumab dose modifications

Starting dose	8mg/kg
Level 1 dose reduction	6mg/kg
Level 2 dose reduction	5mg/kg

Dose modifications will not be required for AEs that are clearly not attributed to TAS 102 or ramucirumab (such as an accident) or for laboratory abnormalities that are not deemed to be clinically significant.

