If a subject experiences a clinically significant and/or unacceptable toxicity, dosing will be interrupted and supportive therapy administered as required.

5.1.1.1 Management for Treatment-Related Toxicity of TAS 102

5.1.1.1.1 Non-hematologic toxicities of TAS 102

Table 3. Non-hematologic toxicity management

Grade¶	Dose hold/resumption within a 28-day treatment cycle	Dose adjustment for next cycle
Grade 1 or 2		
Any occurrence	Maintain treatment at the same dose level	None
Grade 3* or higher		
1 st , 2 nd or 3 rd occurrence	Suspend treatment until Grade 0 or 1	Reduce by 1 dose level from the previous level
4 th occurrence	Discontinue treatment	Discontinue treatment

¶ At the discretion of the investigator, patients may continue on study medication at the same dose without reduction or interruption for AEs (irrespective of grade) considered unlikely to become serious or life-threatening (including, but not limited to, fatigue, alopecia, changes in libido, and dry skin).

* Except for grade 3 nausea and/or vomiting controlled by antiemetic therapy or diarrhea responsive to antidiarrheal medication. Moreover, if grade 4 non-hematotoxicity that is related to the protocol therapy is observed, protocol therapy is to be discontinued. However, in case of adverse events, which can clearly be judged to have derived from the primary disease, depending on the judgement of the investigator (subinvestigator) protocol therapy can be continued. In this case, the reason for this judgement must be recorded in the medical records, etc. (For example: Grade 3 cancer pain that is associated with the primary disease, Grade 3 weight loss that is associated with the primary disease, etc.)

5.1.1.1.2 Hematologic toxicities of TAS 102

Criteria for dose hold and resumption in response to hematologic toxicities related to myelosuppression are described in Table 2.

Uncomplicated neutropenia or thrombocytopenia \leq grade 3 does not require a reduction in dose of study medication. Patients who experience uncomplicated Grade 4 neutropenia or thrombocytopenia that results in a >1 week delay of the start of the next cycle should start the next cycle with dose reduction in $5\text{mg}/\text{m}^2$ step. If toxicity remains despite 4 dose reductions or at a minimum dose ($15\text{mg}/\text{m}^2$ twice a day), discontinue TAS 102.

Table 4. Hematologic toxicity management

Parameter	Hold Criteria		Resumption Criteria*	Dose adjustment for next cycle
	Conventional Units	SI units		

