Neutrophils	<500/mm ³	<0.5x10 ⁹ /L	≥1500/mm ³ (IU: ≥1.5x10 ⁹ /L)	Details below¶
Platelets	<50,000/mm ³	<50x10 ⁹ /L	≥75,000/mm ³ (IU: ≥75x10 ⁹ /L)	Details below¶

* These resumption criteria apply to the start of the next cycle for all patients regardless of whether or not the hold criteria were met. Both conventional and SI (International System) units are presented in CTCAE v. 5.

¶ 1) ≤ Grade 3 neutropenia or thrombocytopenia

- If there are no complications (such as fever, infection or hemorrhage), there is no need to reduce the dose of TAS 102
- If there are complications, the necessity of reducing dose should be considered also with regard to safety.
- For neutropenia, pegfilgrastim or filgrastim can be administered at investigator's discretion.

2) Grade 4 neutropenia or thrombocytopenia

- When there are no complications, but initiation of the next cycle is delayed by more than one week, dose should be reduced by 1 level (Table 1) when starting next cycle (dose is not reduced when administered on the same weekday). If initiation is not delayed by more than one week, the next cycle can be initiated at the same dose level.
- If there are complications, in consideration of the safety of the patient, dose should be reduced by 1 level (Table 1) when starting the next cycle.
- For neutropenia, pegfilgrastim or filgrastim can be administered at investigator's discretion.

5.1.1.1.3 Dose resumption timing of TAS 102

If the patient recovers from the toxicities to the resumption criteria defined above during the 2-week treatment period (treatment Days 1 through 5, 8 through 12), and no dose reduction is required, study drug therapy may be resumed during that cycle.

If a dose reduction is required, study drug therapy should be resumed at the start of the next cycle at the appropriate dose level according to instructions provided in Table 1 and 2. If the study drug dose is reduced, it must not be increased for subsequent cycles.

If the toxicities that are defined above recover during the recovery period (Days 13 through 28), start the next cycle on schedule at the appropriate dose level according to instructions provided in Table 1, 3 and 4.

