If the toxicities that are defined above do not recover during the treatment or rest period, the start of the next cycle can be delayed for a maximum of 28 days from the scheduled start date of the next cycle. If resumption criteria are met by this maximum 28-day delay, start the next cycle at the appropriate dose level according to instructions provided in Table 1, 3 and 4. Patients who

require more than a 28-day delay in the scheduled start date of the next cycle will have study medication discontinued.

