9.2 Determination of sample size

The primary objective of this study is overall survival at 6 months. Overall survival (OS) will be defined as the time from starting on trial to date of death due to any cause. Dropouts/screen failures defined in section 4.3.1. Patients will be considered inevaluable for the primary endpoint of 6 months of overall survival if they are not able to complete first cycle or if they are lost follow-up prior to 6 months from starting on trial except death. Inevaluable patients will be replaced. The study will test the null hypothesis of $\leq 45\%$ of OS at 6 month against the alternative of $\geq 70\%$ of OS at 6 month. The sample size was determined based on the Simon's two-stage minimax design. With one-sided 10% of type I error rate and 90% power, a sample of evaluable 25 patients will be evaluated; 15 in first stage and additional 10 patients in second stage. If 7 or more out of 15 survive 6 months or more, the study goes on the second stage. The experimental treatment will be deemed to have good activity if ≥ 15 out of 25 patients survive 6 months or more. We will continue to recruit patients during interim analysis

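### Table 1 lists two TAS 102 doses at BSA 2.09 m² (25 mg/m² level) and at BSA 2.29 m² (20 mg/m² level): a minor dosing-table error with a near-free fix

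*Combined protocol and SAP*

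**What the plan says.** Table 1 in Section 5.1.1 has four blocks (35, 30, 25 and 20 mg/m²), each split into BSA bands with a dose in mg twice daily and a tablet count. Its footnote reads "Calculate BSA to 2 decimal places".

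The rows at issue are:

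| Block | BSA band (m²) | Dose, twice daily | Tablets per dose |
|---|---|---|---|
| "Level 2 dose reduction: from 30mg/m ² to 25mg/m ²" | 1.90-2.09 | 50 mg | 2 x 15 mg + 1 x 20 mg |
| same block | 2.09-2.29 | 55 mg | 1 x 15 mg + 2 x 20 mg |
| "Level 3 dose reduction: from 25mg/m ² to 20mg/m ²" | 2.10-2.29 | 45 mg | 3 x 15 mg |
| same block | ≥ 2.29 | 50 mg | 2 x 15 mg + 1 x 20 mg |

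The surrounding sections make Table 1 the operative rule. For non-hematologic toxicity of grade 3 or higher, Table 3 (Section 5.1.1.1.1) says "Reduce by 1 dose level from the previous level". For grade 4 neutropenia or thrombocytopenia that delays the next cycle by more than a week, Section 5.1.1.1.2 says "dose should be reduced by 1 level (Table 1) when starting next cycle". Section 5.1.1.1.3 tells the site to "start the next cycle at the appropriate dose level according to instructions provided in Table 1, 3 and 4". None of these gives a rule for a BSA that sits in two rows.

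**The concern.** A table entered with a two-decimal BSA must have bands that share no 0.01 value. These two pairs do, so two patients with the same BSA and dose level can each be dosed according to protocol and still receive different amounts of a cytotoxic drug. Section 10.3 asks for conduct exactly as the protocol describes, which cannot be met where it describes two doses.

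The choice arises at a sensitive moment, when toxicity has just triggered a step down. A patient who starts at 35 mg/m² reaches these blocks after two or three individual reductions. If the six-patient run-in (Sections 3 and 5.1) moves the study to 30 mg/m², patients starting there reach them after one or two. Taking the higher row gives a smaller cut than the change of level implies.

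**Working it through.** **Inputs.** All bands, doses and tablet counts come from Table 1. The number of doses per cycle comes from Section 5.1: twice daily on days 1-5 and 8-12, so 2 x 10 = 20 doses.

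**Step 1: are these the only faults?** Each band was treated as a closed interval and every BSA from 0.80 to 2.99 in steps of 0.01 was looked up at all four levels. Exactly two values return more than one dose, 2.09 at 25 mg/m² and 2.29 at 20 mg/m². No value returns none. The 35 mg/m² block (2.15-2.29, then ≥ 2.30) and the 30 mg/m² block (2.10-2.28, then ≥ 2.29) are clean, so shared limits are not a convention of the table.

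**Step 2: could this be a text-extraction fault?** The tablets add up to the stated dose in all four rows: 2 x 15 + 20 = 50; 15 + 2 x 20 = 55; 3 x 15 = 45; 2 x 15 + 20 = 50. The rows are intact. A misread single digit is unlikely but cannot be wholly excluded.

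**Step 3: size at the overlap.**

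| | BSA 2.09, 25 mg/m² | BSA 2.29, 20 mg/m² |
|---|---|---|
| Exact dose | 25 x 2.09 = 52.25 mg | 20 x 2.29 = 45.8 mg |
| Lower row | 50/2.09 = 23.9 mg/m² (-4.3%) | 45/2.29 = 19.7 mg/m² (-1.7%) |
| Higher row | 55/2.09 = 26.3 mg/m² (+5.3%) | 50/2.29 = 21.8 mg/m² (+9.2%) |
| Ratio of rows | 55/50 = 1.10 | 50/45 = 1.11 |
| Per cycle (20 doses) | 1000 or 1100 mg | 900 or 1000 mg |

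**Step 4: size of the reduction, BSA unchanged.**

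- BSA 2.09: the 30 mg/m² dose is 60 mg (band 1.95-2.09). The nominal cut is 5/30 = 16.7%. Going to 50 mg cuts 10/60 = 16.7%; going to 55 mg cuts 5/60 = 8.3%.
- BSA 2.29: the 25 mg/m² dose is 55 mg. The nominal cut is 5/25 = 20%. Going to 45 mg cuts 10/55 = 18.2%; going to 50 mg cuts 5/55 = 9.1%.

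The higher row therefore delivers about half the nominal reduction in each case.

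**Step 5: can the intended limit be recovered?** At 25 mg/m², yes. The other rows start at 1.10, 1.30, 1.50, 1.70, 1.90 and 2.30, on a 0.20 grid. Each is an exact midpoint between 5 mg steps (25 x 1.90 = 47.5; 25 x 2.30 = 57.5). A start of 2.10 fits (25 x 2.10 = 52.5) and 2.09 does not (52.25). Over BSA 1.00-2.49, all 149 single-row values agree with rounding to the nearest 5 mg.

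At 20 mg/m², no. Rows start at 1.14, 1.35, 1.60, 1.95, 2.10 and 2.29, with no fixed step, and 25 of 149 single-row values depart from nearest-5-mg rounding. For example, BSA 2.30 gets 50 mg although 20 x 2.30 = 46.0 mg. The other blocks offer a precedent for either limit.

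**Step 6: does it reach the statistics?** Section 9.2 states "With one-sided 10% of type I error rate and 90% power, a sample of evaluable 25 patients will be evaluated". The rule (continue if at least 7 of 15 survive, success if at least 15 of 25) gives exact binomial type I error 0.0951 at 45% and power 0.9004 at 70%. Nothing from Table 1 enters that calculation.

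**The case against.** The strongest reply is that this is a copy-edit item. Much of that stands.

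- **Few patients.** The documents give no BSA distribution or reduction rate. Purely as an assumption, if 0.5-2% of patients have a given BSA value and 5-30% reach the level, the expected number per overlap is 25 x 0.005 x 0.05 = 0.006 to 25 x 0.02 x 0.30 = 0.15.
- **Ordinary rounding.** Table 1 already accepts deviations this large where it is unambiguous. At 25 mg/m², BSA 1.09 gets 25 mg (22.9 mg/m², -8.3%) and BSA 1.10 gets 30 mg (27.3 mg/m², +9.1%). At 20 mg/m², BSA 1.13 gets 20 mg (-11.5%) and BSA 1.35 gets 30 mg (+11.1%). Neither disputed dose falls outside those ranges.
- **One overlap is an evident slip.** The 2.09 limit can be corrected from the table's own spacing. The 2.29 limit cannot.

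What the reply does not remove is that the protocol, as written, authorises two doses and gives no way to choose.

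Three stronger readings are tempting, and the documents do not support them.

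- A reader might infer from "If the study drug dose is reduced, it must not be increased for subsequent cycles" that the ambiguity follows a patient through every later cycle. That rule bars escalation. It does not say whether BSA is recalculated; if it is, a change of 0.01 can take the patient out of the overlap, and if the dose is fixed once assigned, nothing remains ambiguous.
- A reader might infer that only patients with two or three prior reductions are exposed. The run-in provision allows a 30 mg/m² start, so one or two can be enough.
- A reader might infer that 45 mg must be the intended dose at BSA 2.29 because the exact dose is 45.8 mg. This block does not follow nearest-step rounding, so that argument does not settle the limit.

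**Conclusion.** The point holds as a minor error, wrong as written. Table 1 gives two doses at exactly two combinations of BSA and level, and nothing else in the protocol resolves them. The consequence is 5 mg per dose, or 10-11% between the two rows, with the higher row giving roughly half the nominal step-down in a patient being reduced for toxicity.

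The step-down comparison assumes that BSA does not change between levels, and the conclusion as a whole assumes that the table text was read correctly. No firm count of affected patients can be given; few or none is the reasonable expectation. The 35 mg/m² and 30 mg/m² blocks and the stated design properties are untouched. It deserves correction because Table 1 is an operative dosing rule, not because it threatens the trial's conclusions.

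**What to change.** - **25 mg/m² block:** change the 55 mg band from 2.09-2.29 to 2.10-2.29. BSA 2.09 then gets 50 mg twice daily.
- **20 mg/m² block:** make the top two rows disjoint, either by starting the 50 mg row at ≥ 2.30 or by ending the 45 mg row at 2.28 and keeping ≥ 2.29. The sponsor should confirm the limit against its source dosing table.
- **Until confirmed:** give 45 mg twice daily at BSA 2.29 on the 20 mg/m² level. The reason is safety, since the lower dose is the more cautious default for a patient being reduced for toxicity.

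With both edits every two-decimal BSA maps to one dose. The cost is one corrected limit and one sponsor query, and no statistical section needs to change.

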5.1.1.2 Management for Treatment-Related Toxicity of ramucirumab

Adverse events of concern which may be related with ramucirumab include are infusion-related reactions, hypertension, arterial or venous thromboembolic events, bleeding (hemorrhagic) events, proteinuria, cardiac events, gastrointestinal perforation, anemia, surgery and wound healing liver injury/liver failure, and reversible posterior leukoencephalopathy syndrome (RPLS). Listed below are guidelines on how to manage these toxicities. Dose reductions of ramucirumab will be allowed only for proteinuria with 6 mg/kg for first episode of proteinuria (2-3 g/24 hours) and with 5 mg/kg for second episode of proteinuria (2-3 g/24 hours) (details on table 2 and **5.1.1.2.4**). Only dose delay will be allowed for the other AEs related to ramucirumab.

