5.1.1.2.4 Proteinuria

If, while on ramucirumab, a patient has proteinuria $\geq 2+$ per a dipstick or routine urinalysis test, ramucirumab will continue as scheduled, and a 24-hour urine collection will be conducted prior to the subsequent scheduled treatment in 2 weeks.

- The following are treatment guidelines for ramucirumab related proteinuria

Proteinuria	Management
< 2g/24hours urine	
 Continue on ramucirumab at the same dose without interruption
2-3g/24hours urine (first episode)	
 Hold ramucirumab for 2 weeks Repeat a 24-hour urine collection prior to next infusion. Resume ramucirumab at a reduced dose level (6 mg/kg every 2 weeks) once the protein level returns to < 2 g/24 hours.
2-3g/24hours urine (second episode)	
 Hold ramucirumab for 2 weeks Repeat a 24-hour urine collection prior to next infusion. Resume ramucirumab at a reduced dose level (5 mg/kg every 2 weeks) once the protein level returns to < 2 g/24 hours.
2-3g/24hours urine (third episode) or >3g/24hours urine	
 Discontinue ramucirumab

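### Section 5.1.1 can be read to allow reduced-dose ramucirumab for proteinuria above 3 g/24 hours, where the table in 5.1.1.2.4 stops the drug

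*Combined protocol and SAP*

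**What the plan says.** Three places in the protocol govern ramucirumab dosing for proteinuria.

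- **Section 5.1.1**, just above Table 2: "Dose reductions of ramucirumab will be allowed only for proteinuria with 6 mg/kg for first episode of proteinuria (> 2 g/24 hours"). The same sentence then lowers the dose once more, to 5 mg/kg, when such an episode recurs, using the identical threshold. It sets no ceiling and does not refer to 5.1.1.2.4. Two general rules in the same section also apply: "The study investigator will determine if either or both medications should be held", and "If a subject experiences a clinically significant and/or unacceptable toxicity, dosing will be interrupted".
- **Section 5.1.1.2** repeats the sentence with a bounded range: "6 mg/kg for first episode of proteinuria (2-3 g/24 hours"). It applies the same bounded range to the 5 mg/kg step and points the reader to Table 2 and to section 5.1.1.2.4.
- **Section 5.1.1.2.4** gives the detailed table. Below 2 g/24 hours the dose is unchanged. For a first or second episode of 2-3 g the instruction is "Hold ramucirumab for 2 weeks", repeat the 24-hour collection, and resume at 6 or 5 mg/kg once protein is below 2 g. The row "2-3g/24hours urine (third episode) or >3g/24hours urine" leads to discontinuation of ramucirumab.

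**The concern.** This is an internal inconsistency in a dosing rule. No design decision is being challenged. The condition for a reduced dose in 5.1.1 has no upper bound, so it overlaps the range in which 5.1.1.2.4 takes the patient off the drug. A reader relying on the summary sentence could resume ramucirumab at 6 or 5 mg/kg in a patient who should have stopped.

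The 24-hour result is the decisive measurement. Under 5.1.1.2.4 it is collected only after a dipstick or urinalysis of 2+ or more, and ramucirumab continues as scheduled in the meantime. Section 10.3 requires the trial to be run as the protocol is written and 8.2.1 has monitors check adherence, so conflicting text also leaves it unclear whether a reduced dose after a result above 3 g is a deviation.

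**Working it through.** There is no sample size, power or error rate to recompute, so the check compares the texts. Each rule was applied to 24-hour results of 1.9, 2.0, 2.5, 3.0 and 3.1 g for episodes 1, 2 and 3, giving 5 × 3 = 15 combinations. The inputs are the thresholds and doses in 5.1.1, 5.1.1.2 and 5.1.1.2.4.

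First or second episode (dose 6 mg/kg for the first, 5 mg/kg for the second):

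| 24-hour protein | 5.1.1 | 5.1.1.2 | 5.1.1.2.4 |
|---|---|---|---|
| 1.9 g | no reduction | no reduction | same dose continues |
| 2.0 g | no reduction (strictly above 2 required) | 6 or 5 mg/kg | hold, then 6 or 5 mg/kg once below 2 g |
| 2.5 g, 3.0 g | 6 or 5 mg/kg | 6 or 5 mg/kg | hold, then 6 or 5 mg/kg once below 2 g |
| 3.1 g | 6 or 5 mg/kg can be read as allowed | no reduction provided for | discontinue |

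Third episode: at 1.9 g nothing changes under any section. At 2.0, 2.5, 3.0 and 3.1 g, 5.1.1 offers no dose and does not mention stopping, while 5.1.1.2.4 discontinues.

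Comparing 5.1.1 with 5.1.1.2.4 over the 15 combinations:

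- Same outcome at 1.9 g: 3.
- Same dose at 2.5 and 3.0 g, episodes 1 and 2: 4. Only 5.1.1.2.4 states the 2-week hold (one dosing interval on the every-2-week schedule) and the recovery condition.
- Different at exactly 2.0 g, episodes 1 and 2: 2. This is a boundary mismatch with 5.1.1 the more restrictive on reduction.
- Different at 3.1 g, episodes 1 and 2: 2. Here 5.1.1 can be read as allowing a dose where the table gives none.
- 5.1.1 silent on stopping, third episode at 2.0 g or more: 4.

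The total is 3 + 4 + 2 + 2 + 4 = 15. The conflict of substance is a first or second episode above 3 g.

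The general safeguards in 5.1.1 do not settle it. Investigator discretion to hold, and interruption for significant toxicity, give no protein level for resuming or stopping, and interruption is not permanent discontinuation.

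**The case against.** The best counter-argument is that the protocol resolves the matter itself. Section 5.1.1.2 restates the sentence with the bounded range and names 5.1.1.2.4 as the place for details, and the table there is unambiguous. The sentence in 5.1.1 only says which toxicity may lead to a reduction and which dose steps exist. It leaves discontinuation to the toxicity-specific subsections: it also allows only delay for other ramucirumab events, yet those subsections require stopping for some of them. It is permissive, so a clinician who stops above 3 g does not breach it. Harm would need an investigator to act on 5.1.1 and miss two later, more specific texts.

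Much of this stands. The intent is reasonably clear, the practical risk is probably limited, and the mismatch at exactly 2 g is minor. It does not remove the conflict. The sentence in 5.1.1 is written as a dosing rule, sits beside the ramucirumab dose table, and has no pointer to 5.1.1.2.4. The table of contents lists 5.1.1 but not 5.1.1.2.4, and section 5.1 directs readers on dose delays to a section 5.1.6 that the contents do not list. A reader can reasonably stop at 5.1.1.

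It can also be objected that copying the hold and stop rules into 5.1.1 would create a second, incomplete version of them. That is a fair drafting point, and the reason why the amended sentence must refer to 5.1.1.2.4 for the full procedure.

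**Conclusion.** The concern holds. For a first or second episode above 3 g/24 hours, 5.1.1 can be read to allow 6 or 5 mg/kg, while 5.1.1.2.4 requires ramucirumab to stop. At exactly 2 g the sections also differ, with little consequence. From above 2 g up to 3 g they agree on dose.

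The text mismatch is certain. Its practical effect is not: the documents give no rate of proteinuria above 3 g, so the number of the 25 patients affected cannot be estimated and may be small. The conclusion that 5.1.1 is the sentence in error assumes that the more specific sections, which agree with each other, express the intent. The 6-month overall survival endpoint and the 7 of 15 and 15 of 25 decision rules are untouched. It should be fixed because it concerns a stopping rule for a named toxicity and errs toward continued dosing.

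**What to change.** In section 5.1.1, replace both thresholds of more than 2 g/24 hours with 2-3 g/24 hours. Then add that ramucirumab is held and resumed at the reduced dose only when protein is below 2 g/24 hours, that it is discontinued above 3 g/24 hours or at a third episode, and that 5.1.1.2.4 governs, including the 2-week hold and repeat collection. If a shorter edit is preferred, the corrected thresholds and the reference to 5.1.1.2.4 are the essential parts.

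The cost is a wording amendment confined to this one rule in 5.1.1, with no added patients, visits or tests.

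### The same-weekday exception in the Table 4 notes has no limit on weeks, so read literally it conflicts with the TAS 102 dose-reduction rule in Section 5.1.1.1.2

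*Combined protocol and SAP*

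**What the plan says.** The rule for uncomplicated grade 4 neutropenia or thrombocytopenia on TAS 102 appears twice in Section 5.1.1.1.2.

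- **Opening text, before Table 4.** A patient whose event "results in a >1 week delay of the start of the next cycle should start the next cycle with dose reduction", in a 5 mg/m² step. No exception is given.
- **Notes under Table 4, grade 4 item.** The trigger is the same: "When there are no complications, but initiation of the next cycle is delayed by more than one week". The action is that the "dose should be reduced by 1 level (Table 1) when starting next cycle (dose is not reduced when administered on the same weekday". The next sentence deals with shorter delays: "If initiation is not delayed by more than one week, the next cycle can be initiated at the same dose level".

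Section 5.1.1.1.3 sets the surrounding limits. The next cycle can be "delayed for a maximum of 28 days from the scheduled start date of the next cycle", and a longer delay ends study medication. If the resumption criteria are met within that limit, staff are told to "start the next cycle at the appropriate dose level according to instructions provided in Table 1, 3 and 4". The dose-adjustment column of Table 4 only points down to the notes, so the notes are the working instruction. On later cycles: "If the study drug dose is reduced, it must not be increased for subsequent cycles".

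Complicated grade 4 events have their own line in the notes, which calls for a one-level reduction with no weekday exception.

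**The concern.** The parenthesis sits inside the sentence about delays of more than one week, so grammatically it can act only on those delays. It names neither a number of weeks nor the weekday it refers to. Within the 28-day limit several restarts fall on the same weekday after more than one week, and for those the two statements of the rule give opposite instructions. Sections 10.3 and 11.1 require adherence to the protocol as written, yet at such a restart staff cannot follow both statements.

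The patients concerned needed two to four extra weeks to recover from grade 4 myelosuppression. Under the literal reading they restart one level higher than the opening text allows. Because a reduction is never reversed, whichever reading is used at that restart carries into later cycles until something else triggers a reduction. Tolerability is a secondary objective, so a uniform reduction rule also helps in interpreting the safety results.

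**Working it through.** No sample-size, power or error-rate figure is involved, so there is no stated figure to reproduce. The check compares the statements of the rule day by day.

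**Inputs**
- Delay d: days from the scheduled start of the next cycle to the actual restart.
- Maximum d: 28 (Section 5.1.1.1.3).
- Cycle length: 28 days (Section 5.1).
- Assumption: the reference weekday is that of the scheduled start. Since 28 = 4 × 7, this is also the weekday of the preceding Day 1 from which the 28 days are counted. Same weekday then means d is a multiple of 7.

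**Rules for uncomplicated grade 4 events**
- A, opening text: reduce if d > 7.
- B, Table 4 note read literally: reduce if d > 7 and d is not a multiple of 7.
- C, Table 4 note as probably intended (the exception means d = 7 only): reduce if d > 7.

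| Days late | A | B | C |
|---|---|---|---|
| 0–7 | same dose | same dose | same dose |
| 8–13 | reduce | reduce | reduce |
| 14 | reduce | **same dose** | reduce |
| 15–20 | reduce | reduce | reduce |
| 21 | reduce | **same dose** | reduce |
| 22–27 | reduce | reduce | reduce |
| 28 | reduce | **same dose** | reduce |

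Rule A requires a reduction on 28 − 8 + 1 = 21 days. Rule B requires it on 21 − 3 = 18. They differ on days 14, 21 and 28 only. Rules A and C differ on no day.

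**Dependence on the assumption.** Days 8 to 28 are three full weeks, so any fixed reference weekday falls among them exactly three times. A different reference would change which days conflict, not how many.

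**Size of the dose difference.** In Table 1, the 35 and 30 mg/m² rows differ by 5 or 10 mg per dose, depending on body surface area. Examples: 60 versus 55 mg at 1.70–1.83 m², and 70 versus 60 mg at 2.00 m². A cycle has 10 dosing days × 2 = 20 doses, so the difference is 5 × 20 = 100 mg or 10 × 20 = 200 mg per cycle.

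**The case against.** The best reply is that nobody would apply the literal reading. It would reduce the dose at day 13, keep it at day 14 and reduce it again at day 15, which has no clinical logic. The natural purpose of the parenthesis is to mark the boundary: the same weekday one week later is exactly one week, not more. Read so, the two statements agree and the flaw is editorial. The days 14, 21 and 28 also depend on a reference weekday that the text does not define, and the Section 6.8 calendar allows ±5 days around Day 1 of later cycles, so the actual previous Day 1 and the scheduled start may fall on different weekdays.

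There are safeguards as well. The resumption criteria (neutrophils at least 1500/mm³, platelets at least 75,000/mm³) apply to every new cycle. Growth factor is allowed for neutropenia. The patient restarts at the level already being taken, never above it. A repeat grade 4 event with a long delay triggers the rule again.

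Most of this stands, and it keeps the point small. It does not rescue the wording. The following sentence already covers day 7, so on the intended reading the parenthesis adds nothing. On the reading its position invites, it contradicts the opening text. It is also in the notes to which staff are sent for the restart dose.

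A reader might infer more, and the documents do not support it:
- That the exception allows restarts at low counts. The resumption criteria rule this out.
- That 3 days in 21 means one affected patient in seven. These are calendar days; the documents say nothing about how restart delays are distributed.
- That the plan deliberately spares patients whose restart falls on a two-weekly ramucirumab visit. No such rationale is given.

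**Conclusion.** The point holds as a minor dosing-safety correction. The parenthesis qualifies the more-than-one-week rule without limiting the weeks. With the scheduled start as reference weekday, its literal reading conflicts with the opening text of Section 5.1.1.1.2 at restarts 14, 21 and 28 days late, and nowhere else from 0 to 28 days. On the likely intended reading there is no conflict, only repetition.

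The conflict is confined to uncomplicated grade 4 neutropenia or thrombocytopenia. Where it applies, the difference is one dose level. The number of patients affected cannot be estimated from the documents. It would be wrong to infer that the trial's conclusions are at risk: the sample size, primary endpoint and decision rule do not depend on this instruction. Confidence is high that the wording is defective; whether any patient would be dosed differently because of it is unknown.

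**What to change.** Delete the parenthesis from the grade 4 item in the Table 4 notes. Alternatively, replace it with: *a restart exactly 7 days after the scheduled date does not count as more than one week*. For uncomplicated grade 4 events the rule then reads the same in both places:

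- up to 7 days late: the same dose is permitted;
- 8 to 28 days late: reduce by one level, or discontinue TAS 102 if the patient is already at the minimum dose;
- more than 28 days late: discontinue, as Section 5.1.1.1.3 already requires.

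The second line needs a single minimum dose. Section 5.1.1 and Table 1 stop at 20 mg/m² twice daily, whereas Section 5.1.1.1.2 names 15 mg/m². The same amendment should state which applies.

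The cost is a short wording change in a protocol amendment. It adds no patients, visits, data or analyses.
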